5.6 Handling of MCF, Fibrinogen Activity and Fibrinogen Antigen values below detection limit

MCF (Maximum Clot Firmness) samples are analysed by central lab. Given that MCF values below the detection limit of “< 2mm” are indicated in the output of the testing as “not measurable”, it was discussed and decided in the BDRM (dated 25-Jun-2020) that for the purpose of the planned descriptive statistical analyses these values will be set to half of the range below the detection limit (range is “0 to 2”, i.e. value used is “1 mm”). In the listings of individual patient data, the MCF output “non measurable” will be presented as “< 2mm” (2 mm is the lower detection limit).

Fibrinogen Activity samples are analysed by local and central lab. Given that Fibrinogen Activity values below the detection limit are indicated by “<” sign before the lower detection limit in the output of the testing, it was discussed and decided that for the purpose of the planned descriptive statistical analyses these values will be set to half of the range below the detection limit.

Fibrinogen Antibody samples are analysed by central lab. Given that Fibrinogen Antibody values below the detection limit are indicated by “<” sign before the lower detection limit in the output of the testing, it was discussed and decided that for the purpose of the planned descriptive statistical analyses these values will be set to half of the range below the detection limit. For values indicated in the output of the testing as “<0.0” the value “0” will be used in the planned descriptive statistical analyses.

6 Patient Accounting and Disposition

6.1 Patient accounting

Based on all enrolled patients, the number and relative frequencies (i.e. percentages) of patients in each study population as defined in section 4 Analysis Sets will be presented by age subgroup and overall for part I. For part II the number and relative frequencies (i.e. percentages) of all enrolled patients will be presented by age subgroup and overall based on the APE set; number and relative frequencies of patients in the SAF, ITT, FAS, and PP sets will be presented based on the SAF set. A listing with patient accounting data will be also presented.

An analogue presentation, including age groups, will be generated showing frequencies and percentages of the event based analysis sets (FBE and PPBE) from part II (ODP or ODT, each for minor events, major events and overall). Note, however, that these reflect events rather than patients. A listing with bleeding event based data will also be presented.

6.2 Disposition and withdrawals

The number and relative frequency (i.e. percentages) based on all enrolled patients (APE) will be presented by study part and overall for

- Patients by site and country (worldwide)
- Patients by site and country (European Economic Area (EEA))
- Patients by age group according to EudraCT

(in utero subjects, preterm newborn infants (gestational age <37 weeks), newborns (0-27 days), infants and toddlers (28 days-23 months), children (2-11 years), adolescents (12-17 years), adults (18-64 years), from 65 years on, from 65-84 years, 85 years and over)

The number and relative frequency (i.e. percentages) based on all enrolled patients (APE) will be presented by age group and overall for

Part I:

- Patients participating in part I (Patients enrolled)
- Patients not eligible (Screen failures)
- Patients eligible
- Patients who prematurely discontinued the study part I before treatment (with reasons for discontinuation)

Part II:

- Patients participating in part II (Patients enrolled)
- Patients not eligible (Screen failures)
- Patients eligible
- Patients who prematurely discontinued the study part II before treatment (with reasons for discontinuation)

- Patients who completed the study without bleeding event (study completion defined as regular study completion/no early termination)

The number and relative frequency (i.e. percentages) based on all treated patients (SAF) will be presented by age group and overall for

Part I:

- Patients treated in part I
- Patients who prematurely discontinued the study part I after treatment (with reasons for discontinuation)
- Patients who completed the study part I (Patient was treated in part I and completed/terminated the study after part I PK safety visit; in case PK safety visit was not done/has no date, date is calculated as 49 days after "PK Dosing Day 0".)

Part II:

- Patients treated in part II
- Patients treated in part I and II
- Patients who prematurely discontinued the study part II after treatment (with reasons for discontinuation)
- Patients who completed the study part II (study completion defined as regular study completion/no early termination)

A listing with all the patient disposition data will be also presented.

For the event based analysis the frequencies of part II bleeding events by patient (total) and additional descriptive statistics for frequencies of events by age group and overall will be presented (mean, SD, min, max, median) for FBE and PPBE. A listing with bleeding event data will be also presented.

6.3 Protocol deviations

The number and relative frequency of patients (and/or events) with protocol deviations (major/minor) will be presented overall for SAF and FAS (part I and part II) and FBE in part II for total and categories. All patients/events with their protocol deviations will be listed.

In the BDRM, dated 25-Jun-2020, all minor and major protocol deviations on patient and on bleeding event level were reviewed and agreed upon. Following from the decisions taken, assignments to analysis populations were done. A complete list of all protocol deviations is attached to the BDRM minutes and included in the listings of the final analysis.

7 Demographics and Background Characteristics

All assessments will be done for part I and II separately.

Assessments made at screening visit and at PK Dosing Day 0 (pre-dose) will be summarized for patients treated with BT524 (SAF) using descriptive statistical methods only. These assessments will include demographic data and medical history as specified below as well as previous or concomitant medications (see section 9 below). Other relevant baseline characteristics from screening visit (such as physical examination, vital signs, etc.) will be presented as part of the applicable safety evaluations or only be listed (such as history of alcohol consumption or smoking).

Summary tables with summary statistics and frequency tables will be presented as appropriate. Graphical presentations will be used if they increase transparency and understanding of the data. Details on what outputs will be produced along with their layout and technical specifications will be provided in the separate tables shell document.

7.1 Demographics

The following demographic characteristics will be presented on patient level for both part I and part II

- Gender (male/female)
- Age (years) at date of first BT524 treatment in the respective study part.
- Race (White, Black, Asian, Other)
- Ethnicity (Hispanic or Latino, Not Hispanic or Latino)
- Weight (kg) at baseline (if documented in lb it will be transformed into kg via:
weight (kg) = weight(lb) x 0.4536, rounded to 2 digits)
- Height (cm) at baseline (if documented in inch it will be transformed into cm via:
height (cm) = height (inch) x 2.54, rounded to 2 digits)
- BMI (kg/m^2) at baseline = weight in kg / (height in cm) 2 x 10000
- Disease characteristics (Afibrinogenemia, severe hypofibrinogenemia)

The following information will be presented on event level for the FBE set

- Age (years) as age at date of each event treatment (Day 0 of part II).

Presentations for event level will be done overall as well as by ODP or ODT.

Presentations will be done overall as well as by age group (0 to 27 days, 28 days to < 2 years, 2 to < 6 years, < 6 years, 6 to < 12 years, 12 to < 18 years, ≥ 18 years).

An additional table will be generated presenting the age classification according to EudraCT (in utero subjects, preterm newborn infants (gestational age < 37 weeks), newborns (0-27 days), infants and toddlers (28 days-23 months), children (2-11 years), adolescents (12-17 years), adults (18-64 years), from 65 years on, from 65-84 years, 85 years and over), but the classification is only presented in the patient disposition part of the analysis.

All patients/events with their demographics data will be listed.

7.2 *Medical history/ concomitant diseases*

The diseases and conditions are coded on a regular base during study conduct and at time of database lock the 2012Q3 version of the WHO Drug Dictionary will be used for the final coding. The medical conditions will be classified as follows:

- Previous medical conditions, i.e. medical conditions that stopped prior to start of first treatment
- Concomitant medical conditions, i.e. medical conditions still present or occurring after start of first treatment

The frequency of diseases recorded from medical history will be presented (SAF) after classification into previous and concomitant conditions by system organ class (SOCs) as well as the frequencies of preferred terms within each SOC. If patients have more than one disease within an SOC or Preferred Term they will be counted only once for the respective SOC or Preferred Term. A listing with all patient medical history/concomitant medical condition data will be also presented.

7.3 *Bleeding history*

On patient level the following analyses will be done:

- Frequencies of bleeding events for Epistaxis, Oral cavity bleeding, Gastrointestinal bleeding, Post-partum bleeding, Umbilical cord bleeding, Menorrhagia, Muscle Haematoma, Haemarthrosis, Intraperitoneal bleeding, Intracranial bleeding, Others, and total.
- Annual bleeding rate = Number of bleedings within the last 12 months before ICF signature (spontaneous, total). Not applicable for patients < 1 year.
- Frequencies of bleedings due to surgical procedure

Descriptive statistics for total number of bleedings and Number of bleedings due to surgical procedure, as well as for annual bleeding rate (based on patients ≥ 1 year at ICF signature) will be presented for each age group and overall.

For patients below 1 year of age total number of bleeds will be given and described in a footnote.

A listing with all patient bleeding history data will be also presented.

8 Exposure and Compliance

All assessments will be done for part I and II separately.

8.1 Treatment groups

Not applicable.

8.2 Dosage

For part I descriptive statistics for the following dose data will be presented for SAF, FAS, PP, PK sets for the overall population and each age group.

- Calculated dose (of fibrinogen) (mg)
- Calculated dose (of fibrinogen) per kg (mg/kg) = Calculated dose (of fibrinogen) (mg)/body weight (kg)
- Calculated volume (mL)
- Volume administered (mL),
- Total dose administered (mg),
- Nominal dose (of fibrinogen) administered (mg) = calculated dose x (volume administered / calculated volume)
- Nominal dose (of fibrinogen) per kg administered (mg/kg) = calculated dose per kg x (volume administered / calculated volume)

For part II (ODP or ODT) descriptive statistics for the following dose data will be presented for FBE and PPBE on event level (ODP or ODT, each for minor events, major events and overall) for the overall population and each age group:

- Target Fibrinogen level (g/L)
- Baseline Fibrinogen level (g/L)
- Total volume administered (mL)
- Total dose administered (mg)
- Total dose administered per kg BW (mg/kg) (will be calculated)
- Number of infusions per bleeding event

In case of repetitive infusions for treatment of one bleeding event (only applicable for part II), all parameters per single infusion will be listed. In addition the mean values of the repeated infusions will be listed for Target Fibrinogen level and Baseline Fibrinogen level and the sum of the repeated infusions will be listed for Total volume administered, Total dose administered, and Total dose administered per kg BW. For the descriptive statistics, the mean of the Target Fibrinogen level and the Baseline Fibrinogen level will be calculated for each patient per bleeding event. These mean values will then be used for the descriptive analysis. For all other parameters in the list above, the sum of single infusions for treatment of one bleeding event will be used for the descriptive statistics.

Descriptive statistics (frequencies and percentages) for treated surgery events will be provided for the FBE set, separated into pre-operative administration, intra-operative administration and post-operative administration.

Descriptive statistics for the FBE set (frequencies and percentages) of number of infusions per bleeding event will also be produced according to no repeated infusion (only one infusion), at least one repeated infusion (at least 2 infusions), and numbers of infusions per bleeding event: 1, 2, 3, >3.

A listing with all patient study medication dosage data will also be presented.

8.3 Treatment/infusion duration

Descriptive statistics for the following treatment duration data will be presented for part I (SAF, FAS, PP, PK) and on event level from part II (for FBE and PPBE) for the overall population and each age group.

- Treatment duration will be calculated in minutes as end of administration (time/date) – start of administration (time/date)
- Infusion rate (mL/min.)

Also descriptive statistics (frequencies and percentages) of changes in infusion rates will be produced according to no change in infusion rates, at least one change in infusion rate, and numbers of changes in infusion rates (per treatment/event): 1, 2, 3, >3. Same evaluation will be done for infusion interruption.

A listing with all patient treatment/infusion duration data will also be presented.

8.4 Compliance

For part I compliance can be assessed by the statistics on calculated dose of fibrinogen per kg (mg/kg) presented within the dosage evaluation (cf. section 8.2 above). For part I, analyses will use actual time, actual dose and infusion rate to derive the different characteristics.

Due to the individually tailored dose for treatment of part II bleeding events no compliance rules based on calculated dose as for part I treatments apply. As the IMP will be administered intravenously to each patient under the supervision of the study investigator or designated qualified study personnel, the compliance is expected to be 100%. In addition, compliance can be assessed based on infusion interruptions (cf. section 8.3 above).

9 Previous and Concomitant Medication or Treatment

All assessments will be done for part I and part II separately for the SAF set.

Previous and concomitant medications are coded according to WHO drug dictionary. version 2012Q3 which will be used at time of database lock and stored with A(natomical) T(herapeutic) C(hemical) codes and generic names.

Treatment will be classified as previous if stopped prior first infusion and as concomitant if overlapping with study participation after first infusion.

The numbers and frequencies of previous and concomitant medications will be given per ATC level 2. If a patient has received more than 1 drug within an ATC class he/she will be counted only once for this ATC class. A listing with all patient previous and concomitant medication or treatment will be also presented.

10 Pharmacokinetics, Pharmacodynamics and Efficacy

All assessments will be done for part I and part II separately.

Unless explicitly specified otherwise efficacy analyses will consist of descriptive methods and not test hypotheses but rather aim at parameter estimation and determination of confidence intervals. Should tests be conducted and/or p-values be given (beyond the one in section 10.2), note that these are not adjusted for multiplicity (which would be needed for fully confirmatory conclusions across all tests given the number of endpoints to investigate).

Also, only descriptive analyses will be performed to compare the efficacy results of study 984 with the results from published clinical trials (cf. protocol section 15.2).

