#### Part I

#### Dosage for the Assessment of the Pharmacokinetics/ Pharmacodynamics of BT524

Each patient fulfilling the inclusion/ exclusion criteria is to receive a fixed dose of 70 mg BT524 per kilogram BW via a single intravenous infusion for the assessment of the pharmacokinetics/ pharmacodynamics of BT524 (see Table 3).

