#### Pre-school Children Group III (2 to < 6 years), Newborns/Infants and Toddlers Group IV (0 days to < 2 years):

BT524 is to be administered intravenously (IV) via an infusion pump with an adapted infusion rate below 5 ml/min (100 mg/minute) according to age, BW, and medical condition at the discretion of the treating physician of the patient (for further details please refer to Appendix 20.1).

Table 3:	Pharmacokinetics:	Dose,	Target	Level,	Mode	of	Administration	and
	Infusion Rate of BT	524						

	Dose of BT524	Target Level	No. of Doses	МОА	Infusion Rate	
Pharmacokinetics						
	70 mg/kg BW		single	IV	5 ml/min* < 5 ml/min** (< 100 mg/ml)	

BW: body weight; IV: intravenous; min: minute; MOA: mode of administration

\* for Adults and Children/Adolescents Group I and Group II ( $\geq$  6 years).

\*\* for Pre-school Children Group III and Newborns/Infants and Toddlers Group IV (< 6 years)

For the assessment of the pharmacokinetics/ pharmacodynamics the total dose will be individually calculated on each patient's BW taking into account the actual activity of BT524 of the batch used as specified in the **COA** as Fibrinogen activity (Precipitation). The corresponding volume to the calculated total dose of BT524 is to be administered according to the following example.

For example: A patient with a BW of 60 kg is to receive a total dose of 4,200 mg BT524 (m). The actual Fibrinogen activity (Precipitation) for the batch used is  $\sim$ 19 g/l according to COA. The volume to be administered is 221.05 ml. Duration of infusion is 44.21 minutes.

 $V_{inf.} = \frac{m (mg)}{c (mg/ml)} = \frac{4,200 mg}{19 mg/ml} = \frac{221.05 ml}{221.05 ml}$ 

Detailed information regarding the prevention of potential risks associated with the administration of BT524 is given in **section 11.7**.

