## Per protocol population (PP)

The PP population consists of all patients of the ITT population, who will have received at least 90 % of the planned total dose of BT524, met all inclusion criteria and none of the exclusion criteria and won't have received any alternative fibrinogen-containing blood product during the specimen collection phase (until day 14).

The PP population will exclude all patients of the ITT population who finish the study with major protocol deviations (e.g. patients who have received any fibrinogen concentrate and/or fibrinogen-containing product within two weeks prior to infusion of BT524) or who terminate the study prematurely due to an event which could be possibly related to the study medication. Classification of protocol deviations as major or minor will be agreed upon between sponsor and study statistician prior to the database lock.

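### SAP 8.4 takes the planned dose per kg as the Part I compliance measure, and that measure cannot register an incomplete infusion

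*SAP*

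**What the plan says.** SAP 8.4 gives one Part I measure: "For part I compliance can be assessed by the statistics on calculated dose of fibrinogen per kg (mg/kg) presented within the dosage evaluation". It adds that Part I analyses use the actual time, dose and infusion rate. It sets no compliance ratio, percentage or threshold.

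SAP 8.2 defines the named measure as the calculated dose in mg divided by body weight in kg. Separately it lists the calculated volume, the volume administered, the total dose administered and an administered counterpart of the named measure: "Nominal dose (of fibrinogen) per kg administered (mg/kg) = calculated dose per kg x (volume administered / calculated volume".

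Protocol 11.1.1 fixes the Part I dose: "dose of 70 mg BT524 per kilogram BW via a single intravenous infusion". The calculation comes before the infusion: "the total dose will be individually calculated on each patient's BW taking into account the actual activity of BT524 of the batch used".

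Protocol 15.2.1 limits the Part I per-protocol population to patients "who will have received at least 90 % of the planned total dose of BT524", among other conditions. The synopsis and section 15.2 give the same 90% figure. The protocol's PK per-protocol population is a subset of that population.

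SAP 4.1.1 defines PP I through the absence of major deviations that could affect the results and gives no dose figure. Its PK set is every Part I patient who has PK data. SAP 2.1 declares consistency with protocol version 6.0, and the changes it lists do not mention the 90% criterion.

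**The concern.** Compliance with a single infusion is a comparison of what was given with what was planned. The measure in 8.4 contains only the planned side. If the site calculates the dose as the protocol directs, every patient has about the same value, so the summary says nothing about delivery.

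Partial infusions are foreseeable: protocol 11.7 provides for stopping the infusion if an allergic or anaphylactic-type reaction occurs. The protocol also makes the received fraction a condition of per-protocol membership, and the SAP text neither repeats that condition nor says it was dropped. Part I is small, with about 15 evaluable patients aged 6 years or older and 3 younger, so one underdosed patient can move an age-group mean in the per-protocol tables of fibrinogen antigen, fibrinogen activity and MCF.

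**Working it through.** **Inputs.** Dose 70 mg/kg, example weight 60 kg, batch activity about 19 mg/ml and rate 5 ml/min (protocol 11.1.1). The two dose-per-kg definitions (SAP 8.2). The 90% limit (protocol 15.2.1).

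**1. Reproduce the protocol's worked example.**
- Dose = 70 × 60 = 4,200 mg.
- Volume = 4,200 / 19 = 221.05 ml. The protocol agrees: "The volume to be administered is 221.05 ml".
- Duration = 221.05 / 5 = 44.21 min, also as stated.

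**2. The 8.4 measure at different weights.** Calculated dose per kg = (70 × BW) / BW:
- 22 kg: 1,540 / 22 = 70
- 43 kg: 3,010 / 43 = 70
- 60 kg: 4,200 / 60 = 70
- 90 kg: 6,300 / 90 = 70

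Weight cancels. Only a rounding or calculation error at the site can move the value.

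**3. The two SAP 8.2 measures when a fraction f is infused (60 kg example).** Volume given = f × 221.05 ml. Nominal dose per kg administered = 70 × f.

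| Fraction infused | Volume given (ml) | Calculated dose per kg (8.4 measure) | Nominal dose per kg administered |
|---|---|---|---|
| 100% | 221.05 | 70 | 70.0 |
| 90% | 198.95 | 70 | 63.0 |
| 75% | 165.79 | 70 | 52.5 |
| 60% | 132.63 | 70 | 42.0 |
| 50% | 110.53 | 70 | 35.0 |

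The protocol's limit corresponds to 0.9 × 70 = 63 mg/kg. The last three rows fall below it, and the 8.4 measure is 70 in all of them.

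**4. A cohort illustration (assumed, not from the documents).** Suppose 3 of 20 patients stop at 50%.
- Mean calculated dose per kg = 70.
- Mean nominal administered dose per kg = (17 × 70 + 3 × 35) / 20 = 64.75.

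Even the administered mean stays above 63 although three patients are below the limit. The minimum in the table would show that someone was low, but not how many, which is why a count below 90% is worth adding.

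**The case against.** The strongest reply is that nothing is lost from the report. The wording in 8.4 is permissive. The same 8.2 tables give the volume administered, the total dose administered and the nominal mg/kg administered for the SAF, FAS, PP and PK sets. SAP 8.3 tabulates duration, infusion rate and interruptions for Part I. Listing 16.6.1 covers dosage, exposure and compliance for every treated Part I patient. The infusion is given in hospital under supervision, and protocol 11.1.2 expects 100% compliance.

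Most of this stands, and it rules out three stronger readings that a reader might infer.

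- **That a partial infusion would be reported as fully compliant, or hidden.** The SAP defines no compliance percentage or category, and the 60% patient would contribute 42 mg/kg to the administered-dose rows.
- **That the 90% criterion was not applied.** PP I was assigned from deviations reviewed at the meeting of 25 June 2020. Its minutes, and the separate plan for the PK parameters, are not among these documents. Silence on a number does not show that it went unused.
- **That the SAP's PK set breaks the protocol's rule.** The protocol attaches 90% to its PP and PK per-protocol populations. The SAP's PK set is a different and broader set.

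The reply does not rescue the named measure. The sentence on actual dose concerns how other characteristics are derived and leaves the compliance measure as written. The remark in 8.4 on using infusion interruptions to judge compliance belongs to the Part II paragraph.

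**Conclusion.** The point holds as a specification error of minor weight. The Part I compliance measure in SAP 8.4 is about 70 mg/kg by construction, so it can detect a wrongly calculated dose but not an incomplete infusion: at 60% infused it is 28 mg/kg above the administered dose (70 − 42). This assumes that sites calculate the dose as the protocol specifies, apart from rounding.

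The protocol's 90% criterion is also absent from the SAP's PP I definition, and its absence is not recorded as a change. That is a gap in the written plan. The documents do not show that any patient was misclassified or that any Part I result is affected, and neither the primary PK analysis nor the confirmatory MCF test depends on the 8.4 sentence.

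**What to change.** - **SAP 8.4:** assess Part I compliance by the nominal dose per kg administered, or by volume administered divided by calculated volume in percent. Add a row with the number of patients below 90% of the planned dose.
- **SAP 4.1.1:** restate the protocol's 90% criterion for PP I, and for any PK per-protocol set in the separate PK plan. If it was dropped on purpose, record that in SAP 2.1.
- **SAP PK set:** leave it unchanged.

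The cost is a few sentences and one table row, since every variable already exists in SAP 8.2. The one further task is to check the PP I assignments made on 25 June 2020 against the 90% figure. The SAP is dated 2 July 2020, so those assignments already existed, and any patient found below the limit would need a documented decision.
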